16.32 Interim Monitoring

An interim analysis with a futility rule will be performed to permit the decision regarding inactivity if there is strong evidence that the proposed treatment is inactive. The interim analysis will be performed after one-half of the required number of events for the primary analysis, or specifically, after 26 events (progressions) are observed on study. At the interim analysis, we will compare the distribution of TTP in the experimental arm (Arm B) to the standard treatment arm (Arm A). If the observed hazard rate of Arm B divided by the observed hazard rate on Arm A ≥ 1 , we will conclude that an advantage for Arm B has not been established and the trial will be terminated early for futility. Termination of the trial for futility at the interim analysis using this rule results in minimal loss of power (<2%) (Wieand et al, 1994).

16.33 Secondary Outcome Analyses

The secondary endpoints listed below will be evaluated in each arm independently and will also be compared between the two arms in an exploratory manner.

16.331 Survival time is defined as the time from registration to death due to any cause. The distribution of survival time will be estimated using the method of Kaplan-Meier within each arm and compared between the arms using a one-sided log-rank test.

16.332 Overall response rate: The overall response rate will be estimated by the number of patients with an objective status of sCR, CR, VGPR, or PR divided by the total number of evaluable patients. All evaluable patients will be used for this analysis. Exact binomial 95% confidence intervals for the true overall response rate will be calculated within each arm and compared between the arms using Fisher's exact test.

16.34 Adverse Events

All eligible patients that have initiated treatment will be considered evaluable for assessing adverse event rate(s). The maximum grade for each type of adverse event will be recorded for each patient, and frequency tables will be reviewed to determine patterns. Additionally, the relationship of the adverse event(s) to the study treatment will be taken into consideration.

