2.2 Secondary Objectives

2.21 To compare the response rate of the standard treatment arm (lenalidomide/dexamethasone) to the experimental arm (lenalidomide/dexamethasone + anakinra).

2.22 To compare the toxicity of the standard treatment arm (lenalidomide/dexamethasone) to the experimental arm (lenalidomide/dexamethasone + anakinra).

2.23 To compare the overall survival of the standard treatment arm (lenalidomide/dexamethasone) to the experimental arm (lenalidomide/dexamethasone + anakinra).

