- 3.22 Acute/chronic infections, open wounds, or any active infection requiring intravenous antibiotic therapy ≤ 12 weeks prior to registration.
- 3.23 Other active malignancy (≤ 3 years) prior to registration.
Exceptions: Basal cell skin cancer or carcinoma-in-situ of the cervix or low-risk prostate cancer after curative therapy
- 3.24 Any of the following because this study involves an investigational agent whose genotoxic, mutagenic and teratogenic effects on the developing fetus and newborn are unknown:
- Pregnant women
 - Nursing women
 - Men or women of childbearing potential who are unwilling to employ adequate contraception
- 3.25 NYHA Class 3 or 4 CHF symptoms
- 3.26 Other concurrent chemotherapy, radiotherapy, or any ancillary therapy considered investigational.
- NOTE:** Bisphosphonates are considered to be supportive care rather than therapy, and are thus allowed while on protocol treatment.

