13.3 Ineligible patients

A patient is deemed ineligible if at the time of registration, the patient did not satisfy each and every eligibility criteria for study entry. The patient may continue treatment off protocol at the discretion of the physician as long as there are no safety concerns, and the patient was properly registered. The patient will go directly to the event-monitoring phase of the study.

- If the patient received treatment, all data up until the point of confirmation of ineligibility must be submitted. Event monitoring will be required per section 18.0 of the protocol.
- If the patient never received treatment, on-study material and the End of Active Treatment/Cancel Notification Form must be submitted. No further data submission is necessary.

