- 15.35 **Pharmacokinetic information:** The absolute bioavailability of Kineret after a 70 mg subcutaneous bolus injection in healthy subjects (n = 11) is 95%. In subjects with RA, maximum plasma concentrations of Kineret occurred 3 to 7 hours after subcutaneous administration of Kineret at clinically relevant doses (1 to 2 mg/kg; n = 18); the terminal half-life ranged from 4 to 6 hours. In RA patients, no unexpected accumulation of Kineret was observed after daily subcutaneous doses for up to 24 weeks. The influence of demographic covariates on the pharmacokinetics of Kineret was studied using population pharmacokinetic analysis encompassing 341 patients receiving daily subcutaneous injection of Kineret at doses of 30, 75, and 150 mg for up to 24 weeks. The estimated Kineret clearance increased with increasing creatinine clearance and body weight. After adjusting for creatinine clearance and body weight, gender and age were not significant factors for mean plasma clearance.
Patients With Renal Impairment: The mean plasma clearance of Kineret in

subjects with mild (creatinine clearance 50-80 mL/min) and moderate (creatinine clearance 30-49 mL/min) renal insufficiency was reduced by 16% and 50%, respectively. In severe renal insufficiency and end stage renal disease (creatinine clearance <30 mL/min), mean plasma clearance declined by 70% and 75%, respectively. Less than 2.5% of the administered dose of Kineret was removed by hemodialysis or continuous ambulatory peritoneal dialysis. Based on these observations, a dose schedule change should be considered for subjects with severe renal insufficiency or end stage renal disease.

Patients with Hepatic Dysfunction: No formal studies have been conducted examining the pharmacokinetics of Kineret administered subcutaneously in patients with hepatic impairment.

15.36 Potential Drug Interactions (USPI Section Drug Interactions):

Warnings and Precautions

Serious Infections – Kineret has been associated with an increased incidence of serious infections (2%) vs Placebo (<1%) in clinical trials in RA.

Administrations of anakinra should be discontinued if a patient develops a serious infection. Treatment should not be initiated in patients with active infections. The safety and efficacy of anakinra in immunosuppressed patients or in patients with patients with chronic infections have not been evaluated.

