16.23 Analysis Plans

All the relevant results pertaining to toxicity, MTD, response, timed endpoints and laboratory correlates will be examined in an exploratory and hypothesis-generating fashion. The small sample size and the heterogeneous patient population associated with phase I studies restricts the generalizability of the results. Any notable statistical result should only be viewed as preliminary evidence for further study in Phase II trials rather than a definitive finding in and of itself. Data will continue to be collected on patients as long as they are trial participants.

16.231 Adverse Events Profile

The number and severity of all adverse events (overall and by dose-level) will be tabulated and summarized in this patient population. The Grade 3+ adverse events will also be described and summarized in a similar fashion. This will provide an indication of the level of tolerance for this treatment combination in this patient group.

16.232 Toxicity Profile

The term toxicity is defined as adverse events that are classified as either possibly, probably, or definitely related to study treatment. Non-hematologic toxicities will be evaluated via the ordinal CTC standard toxicity grading. Hematologic toxicity measures of thrombocytopenia, neutropenia, and leukopenia will be assessed using continuous variables as the outcome measures (primarily nadir) as well as categorization via CTC standard toxicity grading.

Overall toxicity incidence as well as toxicity profiles by dose level, patient and tumor site will be explored and summarized. Frequency distributions, graphical techniques and other descriptive measures will form the basis of these analyses.

16.233 Response Profile

A response is defined to be a sCR, CR, VGPR, or PR noted as the objective status. Response will be evaluated using all cycles of treatment. All patients meeting the eligibility criteria who have signed

a consent form and have begun treatment will be evaluable for response.

Responses will be summarized by simple descriptive summary statistics delineating complete and partial responses as well as stable and progressive disease in this patient population.

Phase II Portion

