16.35 Over Accrual

If more than the target number of patients are accrued, the additional patients will not be used to evaluate the stopping rule or used in any decision making processes; however, they will be included in final point estimates and confidence intervals.

16.36 Data & Safety Monitoring:

16.361 The principal investigator(s) and the study statistician will review the study at least twice a year to identify accrual, adverse event, and any endpoint problems that might be developing. The Mayo Clinic Cancer Center (MCCC) Data Safety Monitoring Board (DSMB) is responsible

for reviewing accrual and safety data for this trial at least twice a year, based on reports provided by the MCCC Statistical Office.

- 16.362 Adverse Event Stopping Rules (These rules apply to Arm A and Arm B independently for patients in the randomized phase II portion of the study): The stopping rules specified below are based on the knowledge available at study development. We note that the Adverse Event Stopping Rule may be adjusted in the event of either (1) the study re-opening to accrual or (2) at any time during the conduct of the trial and in consideration of newly acquired information regarding the adverse event profile of the treatment(s) under investigation. The study team may choose to suspend accrual because of unexpected adverse event profiles that have not crossed the specified rule below.

Accrual will be temporarily suspended to both arms if at any time we observe events considered at least possibly related to study treatment (i.e. an adverse event with attribute specified as “possible”, “probable”, or “definite”) that satisfy either of the following:

- if 3 or more patients in the first 12 treated patients experience a grade 4 or higher non-hematologic adverse event at least possibly related to treatment.
- if after the first 12 patients have been treated, 25% of all patients experience a grade 4 or higher non-hematologic adverse event at least possibly related to treatment

We note that we will review Grade 4 and 5 adverse events deemed “unrelated” or “unlikely to be related”, to verify their attribution and to monitor the emergence of a previously unrecognized treatment-related adverse event.

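### Section 16.34 leaves treated patients later found ineligible out of the phase II adverse event rates; the effect is probably small and of unknown direction, and cheap to remove

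*Combined protocol and SAP*

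**What the plan says.** Section 16.34 gives the population for phase II adverse event rates: "All eligible patients that have initiated treatment will be considered evaluable for assessing adverse event rate(s". It then asks for the maximum grade of each event type per patient, in frequency tables reviewed for patterns.

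Section 13.3 calls a patient ineligible who, at registration, "did not satisfy each and every eligibility criteria for study entry". One missed criterion is enough. The section allows for this coming to light after treatment has begun: "If the patient received treatment, all data up until the point of confirmation of ineligibility must be submitted". It also sends such patients to event monitoring.

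The objective concerned is 2.22: "To compare the toxicity of the standard treatment arm (lenalidomide/dexamethasone) to the experimental arm". Section 16.33 covers survival and response only, so 16.34 is the only phase II analysis text on toxicity. Section 16.31 adds that adverse events count in the final judgement of the regimen's promise.

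Two other safety texts state no eligibility condition. The first limb of the phase II stopping rule in 16.362, which counts only events with a possible or stronger link to treatment, applies "if 3 or more patients in the first 12 treated patients experience a grade 4 or higher non-hematologic adverse event". The phase I plan in 16.231 says that all adverse events "will be tabulated and summarized in this patient population".

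**The concern.** A safety rate normally describes what happened to everyone who received the drug. Section 16.34 instead applies to safety the eligible-and-treated restriction that 16.11 and 16.31 use for time to progression. A patient's toxicity can therefore be recorded and then removed from the reported rate because of a fact about registration.

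The removal need not be neutral. Section 3.12 requires creatinine clearance of at least 30 mL/min. Section 15.35 reports that in severe renal insufficiency and end-stage disease, below that value, anakinra's "mean plasma clearance declined by 70% and 75%, respectively". Section 15.15 says lenalidomide is eliminated mainly by the kidney. Section 3.22 excludes several kinds of infection, among them "any active infection requiring intravenous antibiotic therapy" in the 12 weeks before registration, and 15.36 associates anakinra with serious infections. A patient entered in error on one of these criteria may differ in toxicity risk from the rest. Other criteria, such as the free light chain ratio or the M-protein level, have no evident link of this kind.

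At stake is the accuracy of the toxicity rates by arm, and possibly agreement between the patients monitored under 16.362 and those reported under 16.34.

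**Working it through.** **Step 1: the texts side by side.**

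- 16.34 (phase II rates): eligible and started treatment.
- 16.362 (phase II stopping rule): treated patients in the first limb, all patients in the second; eligibility not mentioned.
- 16.231 (phase I tables): all adverse events in the patient population; eligibility not mentioned, although 16.233 does state it for response.
- 13.3: treated ineligible patients exist in the plan's own terms, and their data are submitted.

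No section returns these patients to the 16.34 rates.

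**Step 2: what is collected on them.** Section 13.3 requires all data up to confirmation of ineligibility, then event monitoring. Footnote 9 of the test schedule (section 4.0) adds a nurse contact 30 days after the last dose, or at the start of subsequent treatment if sooner. Late grade 3 or higher events and serious events at least possibly related, and deaths from any cause, then go on the event monitoring form. Section 10.613 requires deaths within 30 days, and later deaths that are possibly related. None of these rules states an eligibility condition. The notice ending event monitoring is marked as phase I only.

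**Step 3: how many patients.** The plan's own figures come first. Section 16.12 gives 45 evaluable plus 5 additional patients per phase II arm, so 45 + 5 = 50. With phase I, 18 + 2 + 2 × 50 = 120, which matches the stated total. The 5 covers ineligibility, cancellation (never treated), major violation and other reasons together. The number treated and then found ineligible is not given. I assume k from 0 to 5 per arm.

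**Step 4: effect on one arm's rate.** Suppose x of n treated patients have the event, and k are excluded, of whom d had it. The reported rate is (x − d)/(n − k). Take n = 50 and x = 10, an assumed count, so that the all-treated rate is 20.0%.

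- k = 1: 9/49 = 18.4% if that patient had the event; 10/49 = 20.4% if not.
- k = 2: from 8/48 = 16.7% to 10/48 = 20.8%.
- k = 5: from 5/45 = 11.1% (all five had the event) to 10/45 = 22.2% (none had it).

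**Step 5: exclusion unrelated to toxicity.** The expected d is k·x/n, so the expected rate is (x − kx/n)/(n − k) = x/n = 20.0% for every k. With p = x/n, the standard deviation is √[k·p(1 − p)(n − k)/(n − 1)]/(n − k):

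- k = 1: 0.400/49 = 0.8 points
- k = 2: 0.560/48 = 1.2 points
- k = 5: 0.857/45 = 1.9 points

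For scale, the sampling standard error of the 20.0% rate itself is √(0.2 × 0.8/50) = 5.7 points.

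**The case against.** The strongest objection is that this rarely matters. Section 6.31 has eligibility verified before a registration is accepted, 6.33 bars treatment before registration, and 3.12 requires the laboratory values within the preceding 7 days. Treated ineligible patients should be few, and the creatinine clearance example is less likely than it looks. This stands, and it is why the point is small. It does not remove the point, because 13.3 itself provides for such patients.

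The event counts above are assumed, and 16.34 specifies no between-arm test. Both are true. The link to objective 2.22 rests on 16.34 being the only phase II text on toxicity.

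A reader might infer that 16.34 and 16.362 contradict each other. The documents do not go that far. Section 16.362 is silent on eligibility rather than counting ineligible patients expressly, and 16.34 could be read as governing both. The phase I wording is equally silent. It is fair to say only that monitored and reported rates may rest on different patients.

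A reader might also infer that these patients' records end when ineligibility is confirmed, so that only earlier data could be used. Step 2 shows otherwise. Routine cycle-by-cycle reporting may stop then, but late serious events and deaths are still captured.

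**Conclusion.** The point holds as a weakness in the analysis set. As written, 16.34 drops observed toxicity in treated patients later found ineligible from the rates that serve objective 2.22. The likely effect on an arm's rate is small: with 10 events in 50, one exclusion moves 20.0% to 18.4% or 20.4%. Its direction cannot be known in advance, and there is no expected shift if exclusion is unrelated to toxicity. The larger shifts need several such patients and, for 11.1%, five who all had the event. Five per arm is an assumed figure taken from the 16.12 allowance; that section only anticipates it and does not set a limit.

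A reader might infer that safety oversight is impaired or that events go unreported. The documents do not support that. Routine and expedited reporting and the duties in section 10 state no eligibility condition, and the stopping rule does not exclude these patients. The defect lies in the reported rates. Changing it is a cheap improvement.

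**What to change.** In 16.34, define the phase II adverse event set as every patient who received any study treatment, by arm, regardless of later ineligibility. Use all adverse event data collected on them, including late events and deaths reported through event monitoring. Add a footnote giving the number of such patients per arm and noting that their routine cycle-by-cycle reporting may be shorter. Show the eligible-only table as a sensitivity display. Leave the efficacy set in 16.11 and 16.31 unchanged.

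The cost is one sentence, one footnote and one extra table. No new data are needed and the sample size does not change. The downside is that maximum grades may be understated in the added patients if their routine follow-up is shorter; the footnote and the second table let the reader judge that.

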13.0 Treatment/Follow-up Decision at Evaluation of Patient

NOTE (Phase I Only): As of Addendum 5, Anakinra will no longer be provided and all patients will go off study treatment. Event monitoring will no longer be required. Patients may obtain Anakinra commercially and be treated off study

- 13.1 Responding to treatment
Patients who are sCR, CR, VGPR, PR, or SD (or usCR, uCR, uVGPR, uPR) will continue treatment per protocol.
- 13.2 Treatment continuation
In the absence of treatment delays due to adverse event(s), treatment may continue until one of the following criteria applies:
 - 13.21 Progression requiring treatment for active myeloma
 - 13.22 Unacceptable toxicity and ineligibility for retreatment.
 - 13.23 Patient refusal of continued treatment.

All attempts should be made to complete the End of Study procedures if a patient withdraws from the trial early. The patient will then go to event monitoring per Section 18.0.

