The primary goal of this trial is to compare the time to progression of the standard treatment arm (Arm A) to the experimental arm (Arm B). We will conduct a randomized trial comparing the experimental arm against the standard treatment arm. We will enter 45 evaluable patients to each arm of the study using a 1:1 randomization scheme (Pocock et al, 1975). The stratification factors that will be used are listed in Section 5.0. The primary analysis will be a comparison of Arm A to Arm B using a one-sided log-rank test between the two Kaplan-Meier curves. This final analysis will take place after an approximate 24-month accrual period and after 52 total progressions have occurred or the last patient has been followed for at least 2 years (whichever occurs first). Additionally, we assume a constant accrual rate over the course of the study and that we will not have a significant lost to follow-up issue, as historically lost to follow-up rates in Mayo clinic trials have been $< 1\%$. A sample size of 45 evaluable patients per arm (90 total) provides 80% power to detect an improvement in median time to progression from 20 months to 40 months (a hazard ratio of 2.0), using a 1-sided log-rank test at a significance level of 0.05. A final decision regarding the level

of promise for the experimental regimen will take all factors into account including TTP, response rate, OS, adverse events, and other relevant factors. All patients meeting the eligibility criteria who have signed a consent form and have begun treatment will be evaluable for the primary endpoint.

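### Section 16.34 compares phase II toxicity by maximum grade over open-ended treatment, with no time window or exposure measure, so a longer-treated experimental arm could look more toxic at equal event rates

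*Combined protocol and SAP*

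**What the plan says.** - Objective 2.22 is "To compare the toxicity of the standard treatment arm (lenalidomide/dexamethasone) to the experimental arm (lenalidomide/dexamethasone + anakinra").
- Section 16.33 gives between-arm methods for survival and response only. Adverse events are left to 16.34: "The maximum grade for each type of adverse event will be recorded for each patient, and frequency tables will be reviewed to determine patterns". The denominator is patients: "All eligible patients that have initiated treatment will be considered evaluable for assessing adverse event rate(s"). Section 16.34 adds that relationship to treatment will be considered. It names no window, per-cycle rate, time to first event or between-arm test.
- Under 13.2, "treatment may continue until one of the following criteria applies": "Progression requiring treatment for active myeloma", "Unacceptable toxicity and ineligibility for retreatment", or patient refusal. No number of cycles is set.
- The design in 16.31 assumes exponential TTP with medians of 20 months (len/dex plus placebo) and 40 months (len/dex plus anakinra).
- The sentence in 16.31 that begins "A final decision regarding the level" lists adverse events, along with TTP, response rate and OS, among the inputs to the judgement on the regimen's promise.

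**The concern.** A maximum-grade table counts whether a patient ever had an event of a given grade. Without a window, that proportion depends on the event rate and also on how long each patient was observed on treatment. The trial is built on the hypothesis that one arm stays progression-free twice as long, and progression is one of the main reasons to stop treatment. If the hypothesis is true, the arms are probably not observed on treatment for the same time. Events that build up over months of len/dex, such as infection or thromboembolism, could then be more frequent in the experimental arm with no contribution from anakinra. Since 16.31 weighs adverse events in the final judgement, that gap could be read as a cost of anakinra. Considering attribution, as 16.34 does, would not remove it: events caused by len/dex are truly treatment-related in both arms.

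**Working it through.** **Inputs from the documents.** Medians 20 and 40 months, exponential model, 1:1 allocation, 45 evaluable patients per arm, one-sided alpha 0.05, 80% power, constant accrual over about 24 months, negligible loss to follow-up, final analysis at 52 progressions or 2 years after the last patient (16.31).

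**Reproducing the plan's own figures.**
- Schoenfeld events: 4 × (1.645 + 0.842)² / (ln 2)² = 51.5, so 52. Power at 52 events is 80.4%.
- Hazards: λA = ln 2/20 = 0.03466 and λB = ln 2/40 = 0.01733 per month. At 24 months, exp(−24λ) = 43.5% and 66.0%, matching the stated 43% and 66%.
- At month 48, follow-up c is uniform on 24 to 48 months. P(progressed) = 1 − [exp(−24λ) − exp(−48λ)]/(24λ) = 0.7045 (A) and 0.4602 (B). Expected events: 45 × (0.7045 + 0.4602) = 52.4. The 52nd is expected at about month 47.5, so the two triggers nearly coincide.

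**Mean time to progression or cut-off** = P(progressed)/λ.
- A: 0.7045/0.03466 = 20.3 months. B: 0.4602/0.01733 = 26.6 months. Ratio 1.31 (1.30 at the 52-event date).

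This equals time on treatment only if progression is the sole reason to stop. The documents give no rate for other stopping, so the following are assumptions:

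| Scenario | Excess time at risk, B over A |
|---|---|
| Progression the only reason to stop | 31% |
| Common extra stopping, 10% per year | 28% |
| 20% per year | 26% |
| 30% per year | 24% |
| 50% per year | 19% |
| Only the first 24 months counted | about 21% |
| True hazard ratio 1.5, no other stopping | 19% |

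**Effect on the maximum-grade table.** Assume a constant on-treatment event rate h, equal in both arms, and a common extra stopping rate d. With k = h + λ + d, the proportion with at least one event is (h/k) × {1 − [exp(−24k) − exp(−48k)]/(24k)}.

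Example with h = 1% per month and d = 0:
- A: k = 0.04466; 0.2239 × (1 − 0.2101) = 17.7%.
- B: k = 0.02733; 0.3659 × (1 − 0.3806) = 22.7%.

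| h per month | A | B | False excess, d = 0 | False excess, d = 2% per month |
|---|---|---|---|---|
| 1% | 17.7% | 22.7% | 5.0 points | 3.3 points |
| 2% | 31.1% | 39.1% | 8.0 points | 5.4 points |
| 3% | 41.4% | 51.2% | 9.8 points | 6.7 points |

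**Where it shrinks.**
- Declining hazard (illustrative Weibull, shape 0.5, no other stopping): 21.1% vs 24.4%, and 33.3% vs 38.1%, a gap of 3-5 points.
- Events confined to the first month: relative inflation under 1%. Section 1.3 places injection site reactions there.

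**Effect of a common window.** Time at risk within a window of w months is (1 − exp(−λw))/λ. At 6 months it is 5.42 vs 5.70 (ratio 1.05). At 12 months it is 9.82 vs 10.83 (ratio 1.10), and the false excess for h = 1-3% falls to about 1-2 points. Under a constant rate, events per unit of time on treatment have ratio 1.0.

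**The case against.** The strongest reply is that TTP is not treatment time. Section 13.21 ends treatment at progression that requires treatment for active myeloma. Table 11.5 allows progression on an M-protein rise alone, and smoldering and indolent patients are eligible, so a TTP event need not end treatment. Section 7.5 allows a taper of lenalidomide and/or dexamethasone after 2 years at plateau, 7.4 allows interruption for stem cell collection, 16.11 anticipates subsequent therapy before progression, and dose reductions under Section 8 may lower later risk. This stands. A reader might infer that the experimental arm will have 30% more exposure, but the documents do not give exposure in either arm, and 30% is the upper end of a scenario range.

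A second reply is that 16.34 is descriptive. This also stands. A reader might infer that an effective regimen would be marked down, but no rule turns the table into a penalty, and 16.31 puts TTP beside adverse events. At 45 per arm, a gap of 5.0 to 9.8 points is about 2 to 4 patients, against a standard error of about 8 to 11 points; the artefact alone would reach two-sided significance at 0.05 only about 9-15% of the time. But 16.34 has no test to act as a filter, so such a gap would be read by eye.

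A third inference would be that early stopping of anakinra hides its toxicity. The direction is possible, but the documents give no basis to size it, and they partly guard against it. All eligible treated patients are counted, so the event that led to stopping is kept. Patients who stop one agent stay on study unless all are stopped (notes after 8.4). Late grade 3+ and serious events at least possibly related to treatment are sought at 30 days (Section 4.0, footnote 9).

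Finally, safety during the trial rests on the arm-specific stopping rules and DSMB review in 16.36, not on 16.34. That is so, and this point concerns only the final comparison.

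**Conclusion.** The point holds as a gap in the final toxicity comparison. Section 16.34 offers one measure for objective 2.22, and that measure mixes event rate with time on treatment. If the design hypothesis is true and treatment time roughly tracks TTP, the experimental arm has up to about 30% more time at risk. Allowing for other stopping, or counting only the first 24 months, gives about 20-28% (19% at the heaviest stopping rate assumed), and a smaller true effect gives less. Equal, steadily accruing event rates would then show as roughly 3-10 points more in the experimental arm. The excess is smaller if the hazard declines and negligible for first-month events. These sizes rest on the exponential model, equal event rates and assumed stopping rates. The risk is misreading in the 2.22 comparison and the 16.31 judgement. Stopping patterns that differ between arms could push the bias the other way, by an amount that cannot be estimated from the documents.

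**What to change.** Amend 16.34. Keep the whole-treatment maximum-grade table as description, and base the between-arm comparison for 2.22 on two added measures, with treatment duration by arm shown alongside:

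- (a) Grade 3+ and serious event rates per patient-cycle on treatment, by arm. State how repeat events are counted and whether a cycle on any study agent counts.
- (b) Maximum grade within a common early window, for example the first 6 or 12 cycles. These leave about 5% or 10% excess exposure under the design assumptions.

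State in 16.31 that these measures supply the adverse event part of the final judgement.

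The cost is SAP wording and a few tables. Adverse events are already collected at the end of each cycle (7.6), and the treatment, adverse event and end-of-treatment forms already exist (18.12). Sample size, visits, treatment and the primary analysis are unchanged. The limitation is that per-cycle rates assume a roughly constant hazard, which is why the early-window table should accompany them.
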